#### **4.5. Main analysis.**

The aggregate statistics for continuous variables will include the number of observations (N), the mean value, the standard deviation (SD), the minimum value, Q1 (25th percentile), median, Q3 (75th percentile), maximum value, interquartile range. Tables of categorical variables will represent all possible categories and will display the number of observations for each category, as well as percentages. Precision for percent is one decimal point, if the denominator is less than 100 (in all columns), in this case, percentages are indicated by integers. In general, the percentages will be calculated based on the total number of patients in the analyzed population, regardless of

whether they have missing values or not. The category "Missing" will be displayed when at least one patient falls into this category. The CRF contains several nested questions (that is, questions that require more detailed information only in a subset of patients with a specific value for another question, "if yes" questions); for these variables, percentages will be based on patients with a corresponding value for a higher-level issue, rather than using all patients in the population as reference values.

#### **4.6. Further analysis**

In the case of the availability of data on patient, which are observed in parallel in other registries, it is necessary to perform an analysis for this group separately from the rest of the patients. In the event of a discrepancy between the indicators of other registers and this study, the latter is determinative.

#### **4.7. Quality control**

The Analytical Working Group and the Technical Operator and the Personal Data Operator will check the data for completeness and correctness, inform the local executors about probable errors and omissions in the data when filling CRFs by the doctors. Obvious corrections will be made at the level of administrators and managers of the system who are employees of LLC "RSMI" with notification to the curators of the register.

The Quality Management System (QMS) of RSMI LLC standardizes the procedures for creating and maintaining patient databases on the basis of a universal software package for medical organization and information for the collection, dynamic clinical and epidemiological surveillance and analysis of data in remote access mode ROSMED.INFO. QMS ensures the fulfillment of the customer's requirements and the conformity of the processes and their results with the legislation of the Russian Federation.

LLC "RSMI" guarantees the availability of personnel, production environment and appropriate infrastructure for the implementation of QMS.

LLC "RSMI" within the framework of the QMS ensures that the organization's knowledge base, the level of sufficient competence of the employees involved in the work process and their awareness of the standards of the quality management system are adequate to the work objectives and objectives.

LLC "RSMI" guarantees the availability of functioning internal and external communications that ensure the operation of the quality management system. The QMS of the organization regulates the analysis of requirements related to the company's products and services. QMS LLC RSMI includes all stages of development and maintenance of the software product and databases, including the stages of statistical processing of the results obtained through the integrated online statistical processing module.

#### **4.8. Limitations of study methods.**

The following errors must be taken into account when planning methods for recruiting patients and their follow-up observation:

- Wrong information;
- Incorrect inclusion of the patient in the study;
- Errors in the periods of entering information;
- Removal of the patient at the stage of the beginning of the period of dynamic observation.

In order to reduce the likelihood of these errors within the QMS (quality management system), it is planned to conduct audits for compliance of the RSAR data with the study protocol, the requirements of the study organizers and the legislation of the Russian Federation. The program includes built-in internal validation tools for the entered data. To minimize the risks of mistaken inclusion of patients, the process of registration of patients in the study will be extremely consistent. All patients who meet the inclusion criteria, regardless of location (research base) will necessarily be included in the RSAR. Patients participating in interventional clinical trials will not be included. For the entire population entered in the RSAR, the initial characteristics (primary endpoints) will be examined and analyzed. At each base included in the study, a patient screening log will be kept, including information on the field, age, date of birth, the date of diagnosis of AE of serious gravity, the reason for including the patient / reason for not including the patient in the register, the date of signing the informed consent form for participation in the research, reasons for refusing to participate in the register.

The study monitors will have the opportunity to check the sequence of patients' inclusion in the study. The investigators and organizers of the RSAR will make every effort to minimize unreasonable drop-out of patients from the register, within which regular contact will be made with the patient / his legal representative, in case of dropout, the cause will necessarily be established (with documentary evidence, about death). A signal for an emergency contact with the patient / legal representative will be the miss of another planned visit within the framework of the visit. The contact form and its result will be registered in accordance with the established procedure (SOP LLC RSMI).

In order to minimize the dropout of patients, the following efforts will be made:

- Work with databases where patients are recruited;
- Minimizing the difficulties of participation in the register for patients;
- Constant contact of the researcher with the patient.

To study the effects of dropping out of patients during the observation process, parameters such as the number of patients left in% and the reasons for their departure will be summarized and analyzed. Population characteristics will be summarized for the retired patients, compared with the characteristics of patients who have reached the end of the observation period. The period of time for which the patient has left the observation ahead of schedule will be studied and analyzed.

To exclude the shift in the periods of entering information in the form of the patient's IRC, questions of a clarifying character will be present, with reference to a certain frequency of the event, a time interval, etc.

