### 3.0. METHODOLOGY

### 3.1. Registry Design

The Russian Severe Asthma Registry is a prospective multicenter, non-interventional observational study for patients with severe bronchial asthma (SA).

All patients included in the RSAR platform will be periodically observed during routine visits to the hospital with a follow-up of up to five years.

In the RSAR conductance there is no provision for any intervention in routine clinical practice, including the use of the study therapy / treatment methods or special research methods. From the day the project begins, the physician will collect data on all patients with SA who have visit as outpatient or hospitalized patient and who meet the inclusion criteria for in this study.

The study includes a retrospective part - an analysis of the medical records of patients available at the time of their inclusion in the study.

Patients with a confirmed diagnosis of SA (according to inclusion criteria) will be included in the study sequentially and observed for 5 years.

The period of patient's inclusion - from 03.2018 till 11.2022.

The observation period is from 03.2018 till 11.2022.

The approximate period of the Registry work is from 03.2018 to 12.2022.

The target sample size is up to 7,000 patients with SA over a period of 5 years.

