### 3.2. Draft Cities Initiation

The participation of cities and recruitment of patients in the RSAR is expected:

Period, years	Number of participating cities (health facilities)	Number of SA patients CRFs
03.2018-12.2018	30 (100 health facilities)	2000
01.2019-12.2019	30 (100 health facilities))	2000
01.2020-12.2020	30 (100 health facilities))	1000
01.2021-12.2021	30 (100 health facilities)	1000

01.2022-11.2022	30 (100 health facilities))	1000
-----------------	-----------------------------	------

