The data of patients dropped out of the register during the observation will be analyzed and used to calculate the primary points, if the number of completed visits allows, the data can be used to analyze part of the parameters of the observation period. The initial characteristics of patients dropped out of the register before its completion will be compared with the characteristics of patients with a fully completed observation period, taking into account the proportionality of the data (the number of "dropped out" patients).

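### The drop-out checks in 4.4 and 4.8 ignore entry date and time at risk, so the crude percentage matches no stated follow-up year and the comparison with completers is confounded by entry date

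*Combined protocol and SAP*

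**What the plan says.** Section 4.8 (Limitations of study methods) sets out how the effect of drop-out will be studied: "parameters such as the number of patients left in% and the reasons for their departure will be summarized and analyzed". Leavers' characteristics are then to be "compared with the characteristics of patients who have reached the end of the observation period". Section 4.4 (Statistics analysis) has the same comparison: baseline characteristics of leavers "will be compared with the characteristics of patients with a fully completed observation period", with a remark about proportionality that it explains as the number of drop-outs. Section 4.8 also promises to analyse how long patients stayed before leaving early, but names no method.

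The time frame is in section 3.1 (Registry Design). On entry: "The period of patient's inclusion - from 03.2018 till 11.2022". On follow-up: "The observation period is from 03.2018 till 11.2022". The same section states: "Patients with a confirmed diagnosis of SA (according to inclusion criteria) will be included in the study sequentially and observed for 5 years". Section 3.2 gives the expected intake by period under the column "Number of SA patients CRFs": 2000, 2000, 1000, 1000 and 1000. The secondary objectives in section 2.2 report most outcomes at years 1, 2, 3 and 4.

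**The concern.** Entry is spread over the whole observation window. A patient entered in spring 2018 has more than four years in which to leave; one entered in autumn 2022 has a few weeks. A single percentage of patients who left averages over these unequal exposures, so it is not the drop-out risk at any of the yearly time points being reported. Splitting patients into leavers and completers also sorts them by entry date, whatever their reason for leaving.

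At stake is how far the year 1 to 4 results can be trusted. These summaries are the plan's stated means of judging whether loss has distorted them. Read at face value, they could make year 4 look better retained than it is, make years 1 and 2 look worse, and present calendar change in the intake as selective loss, or conceal selective loss behind it.

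**Working it through.** **Inputs from the plan.** Window: 03.2018 to 11.2022 inclusive, 57 months (3.1). Intake: 2000 + 2000 + 1000 + 1000 + 1000 = 7,000 (3.2), which reproduces the target in 3.1.

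**Assumptions.** The documents give no drop-out rate. I assume each CRF in 3.2 is a new patient, entry is even within each period, and drop-out is random at the same annual rate r for everyone, with r from 3% to 20%. The intake periods then cover months 0–10, 10–22, 22–34, 34–46 and 46–57.

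**Step 1: who can reach each year.** Year k is reachable for entry up to month 57 − 12k. With no drop-out at all:
- year 1 (month 45): 5,000 + 1,000 × 11/12 = 5,917 (85%)
- year 2 (month 33): 4,000 + 1,000 × 11/12 = 4,917 (70%)
- year 3 (month 21): 2,000 + 2,000 × 11/12 = 3,833 (55%)
- year 4 (month 9): 2,000 × 9/10 = 1,800 (26%)
- year 5 (month −3): 0

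The two possible meanings of the end of observation therefore behave very differently. If it is each patient's own 5 years, the comparison group is empty. If it is 11.2022, anyone not lost by then is a completer, however short the follow-up. Steps 2 to 4 use the second meaning.

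**Step 2: crude percentage by entry period.** A patient entering at month t has left by 11.2022 with probability 1 − (1 − r)^((57 − t)/12). Averaged within each period at r = 10%:

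| Entry period | Entered | Left | Leavers | Still in |
|---|---|---|---|---|
| 2018 | 2000 | 36.6% | 733 | 1267 |
| 2019 | 2000 | 30.2% | 604 | 1396 |
| 2020 | 1000 | 22.4% | 224 | 776 |
| 2021 | 1000 | 13.8% | 138 | 862 |
| 2022 | 1000 | 4.7% | 47 | 953 |
| All | 7000 | 24.9% | 1746 | 5254 |

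The annual rate is identical in every row; only the time at risk differs.

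**Step 3: crude percentage against cumulative drop-out, 1 − (1 − r)^k.**

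| r | Crude | Year 1 | Year 2 | Year 3 | Year 4 |
|---|---|---|---|---|---|
| 3% | 8.2% | 3.0% | 5.9% | 8.7% | 11.5% |
| 5% | 13.3% | 5.0% | 9.8% | 14.3% | 18.5% |
| 10% | 24.9% | 10.0% | 19.0% | 27.1% | 34.4% |
| 15% | 35.2% | 15.0% | 27.8% | 38.6% | 47.8% |
| 20% | 44.1% | 20.0% | 36.0% | 48.8% | 59.0% |

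The crude figure equals cumulative drop-out at ln(1 − crude)/ln(1 − r) years. For r = 10% that is ln(0.751)/ln(0.9) = 2.7 years, and it lies between 2.6 and 2.8 years across the whole range. In simulated registries at 5%, 10% and 20%, a Kaplan–Meier estimate with patients still in at 11.2022 censored recovers the year 4 column.

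**Step 4: the comparison.** At r = 10%, 2018 entrants are 733/1746 = 42% of leavers and 1267/5254 = 24% of those still in. For 2022 entrants the shares are 47/1746 = 3% and 953/5254 = 18%. The effect on a baseline characteristic depends on its calendar trend (all trends assumed):
- no trend: no difference
- linear rise from 15% to 25% over the window: a false gap of 1.8 percentage points
- linear rise from 10% to 30%: a false gap of 3.5 points
- 5, 10, 15, 20, 25% by entry period: 170/1746 = 9.7% in leavers against 730/5254 = 13.9% in those still in

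In simulations with random drop-out, a person-time comparison stratified by entry year flagged a difference about 5% of the time (4.6% to 5.9%), with or without a trend.

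**The case against.** Several points on the other side are sound.

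- **The list in 4.8 is open-ended, and time to leaving is to be analysed.** True, and a suitable method there would solve the attrition part. But none is named, no censoring rule is given, and the analysis is not linked to the comparison. Describing leaving times among leavers alone repairs neither summary. The proportionality remark in 4.4 concerns the number of drop-outs, not their entry date.
- **Completion may be meant per patient.** Section 3.1 supports that meaning as much as the calendar one. The completer mix in step 4 then does not apply, but the comparison group is empty, so the check fails in another way.
- **The study is descriptive and the primary objective is measured at enrolment.** Both true. Drop-out cannot touch the primary result, and the issue is misleading description rather than test error.

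A reader might also infer more than the documents support. The crude percentage does not understate attrition in general; at years 1 and 2 it overstates it. The comparison does not create false differences for every characteristic, only for those that vary with entry date. Item 104 of the appendix expects new biologics to be added to its list, which makes a trend in biologic use plausible, but gives no rate of uptake. Nor are deaths simply merged with other losses: 4.8 requires the cause of each drop-out to be established, with documentary evidence of death, and reasons to be summarised.

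**Conclusion.** The point stands in limited form. As written, the two drop-out summaries ignore unequal time at risk, and the end of observation that the comparison depends on is undefined. Sections 3.1, 4.4 and 4.8 must be reconciled on it.

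Under random drop-out the crude percentage describes loss at about 2.6 to 2.8 years. At 10% a year it is 5.9 points too high for year 2 (24.9 − 19.0) and 9.5 points too low for year 4 (34.4 − 24.9), while at year 3 the shortfall is only 2.2 points. Leavers are mostly early entrants by design, so the comparison is unreliable for baseline characteristics that trend with calendar time and sound for those that do not. The sizes rest on assumed drop-out rates, assumed calendar trends, even entry within periods and CRFs counting new patients. That the summaries ignore time at risk does not depend on these assumptions. The change should be made because the year 1 to 4 secondary results rely on this check.

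**What to change.** In 3.1, 4.4 and 4.8:

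1. Define the end of observation once, and use that definition in all three sections.
2. Treat patients still followed at 11.2022 as administratively censored.
3. Specify the promised time-to-leaving analysis as cumulative incidence of drop-out at 12, 24, 36 and 48 months from inclusion, by reason, with death as a competing event.
4. Replace the completer comparison. For each year k, compare baseline characteristics of patients who left before year k with those still observed at year k, only among patients whose entry date allows k years, stratified by entry year.

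The cost is protocol wording and somewhat more analysis. Visit dates are collected (appendix item 3), and 4.8 already calls for the cause and timing of leaving, so no new data collection is apparent. The year 4 comparison will rest on at most about 1,800 patients, and the attrition figures for years 3 and 4 will look less favourable than the crude one, while those for years 1 and 2 will look better.

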## **5. 0. Other aspects of the study**

### **5.1. Data quality assurance**

The quality assurance guarantee will cover the following areas:

- guarantee of data quality assurance;
- guarantee of quality assurance of all procedures that are relevant to the RSAR;
- guarantee of software quality assurance and computer systems.

In order to guarantee the quality of the data, measures will be taken to prevent, detect and correct the following types of errors:

- Interpretation or coding errors;
- errors in data entry, accuracy of their transfer and transformation;
- semantic errors;

Activities (steps) to ensure the quality of information will include:

- trainings (training of those responsible for collecting information);
- checking the completeness of the information provided (the presence of an immediate feedback mechanism with the clinical center, where patients are included in the study and observed);
- checking consistency of data (comparing data from different centers and at different time intervals);
- local audit in each center (checking of the screening logs, procedures, data samples);
- special audits (for the centers that cause the greatest fear of inaccurate information entry and are characterized by the greatest number of errors);

In order to ensure the quality of all data on the register, the following will be done:

1. Appointment of the person responsible for the quality of the data in each center included in the study;
2. Scheduled audits of data quality;
3. Activities to maintain and improve the level of competence of staff;
4. Checks security systems and data integrity;
5. Guarantee of the validity of computer systems and software, their compliance with quality and safety standards, compliance with the legislation of the Russian Federation;
6. Information Systems Security Plan;
7. Differentiation of access rights to the patient / legal representative, physician, system administrator, database operator.

Quality assurance of audit can be carried out by representatives of the organizer of the register, and also other authorized regulating bodies. The quality control auditor has access to all medical records related to the research, the researcher's medical files, correspondence and documentation, informed consent of this study.

## **5.2. Data registration**

CRFs for individual patients will be provided to the curators of the project on paper and in digital form.

RSAR will consist of a two-level collection of standardized data, as described below:

- A list of the main variables (defined by the process within the Medical online platform ROSMED.INFO): it will consist of approximately 100 basic variables.
- Extended variable list: this will make all variables useful for scientific research and maximum data collection and create an optimal list of variables. Long-term variables will be collected through standardized joint modules. The name of several: asthma control (ACQ6), a professional history questionnaire, concomitant diseases, a history of vaccinations and biomarkers of severe asthma.

## **5.3. Data ownership**

Based on the results of the study, biostatistical analyzes (customized) of the RSAR data obtained on an annual basis and interim reports every six months will be compiled.

A number of publications are planned on the basis of the statistical analysis of the research data, the authors' team, the internal editing and review procedures will be decided within the working group on the publication policy. The timing of publications and their content will be regulated by the steering committee, the curators of the study.

The rights to intellectual property belong to the Interregional Public Organization "Russian Respiratory Society".

## **5.4. Data access and subordination**

To begin work of RSAR, it is necessary to obtain approval from the independent ethical committee (NEC).

To gain NEC approval it is necessary to provide following documents:

1. The study protocol.
2. Patient's voluntary informed consent form and Information form for the patient.
3. Biography of scientific curators / experts.
4. Documents confirming the legality of the collection, storage and processing of personal data of participants (doctors and researchers).
5. List of clinical centers participating in the study.
6. Public contract-offer (User agreement), documentation in the framework of the policy regarding the organization and processing of personal data.
7. Case Report Form (eCRF).

8. Documentation that confirms the agreement between the supervising organization and the technical contractor of the project for joint work.

The initiation of the work of the Registry is possible only in case all the necessary legal documents are available, and the NEC approves it in accordance with Russian and international legal norms. The same situation applies to the mechanism for introducing changes and amendments.

To participate in the study, the patient/legal representative must sign an informed consent for participation in the study.

Each signature must be dated personally by the signer and retained for the duration of the study, as well as the form of informed consent and any other documents relevant to the patient. A copy of the signed informed consent, as well as any other additional information about the patient, must be provided directly to the patient or his legal representative.

The patient should be informed that his personal data will be used in accordance with Federal Law No. 152 "On Personal Data". The patient should also be explained the level of disclosure within the framework of possible audits by the organizers, curators, research sponsors and technical support parties.

Identification and authentication measures should ensure that unique characteristic (identifier) will be performed to access objects and access objects, a comparison of the identifier presented by the subject (object) with a list of assigned identifiers will be made to verify that the identifier presented to the subject is authentic (authenticated).

**Access control measures should provide management of rights and privileges of access subjects, delineate access of access subjects to access objects based on the set of access control rules established in the information system, and ensure compliance monitoring of these rules.**

Measures to protect computer personal data carriers (means of processing (storing) personal data, removable computer personal data carriers) should exclude the possibility of unauthorized access to computer media and personal data stored on them, as well as unauthorized use of removable personal data carriers.

Measures to register security events should ensure the collection, recording, storage and protection of information on security events in the information system, as well as the ability to view and analyze information about and respond to such events.

Anti-virus protection measures must ensure that computer programs or other computer information is detected in the information system for unauthorized destruction, blocking, modification, copying of computer information or neutralizing information protection means, as well as responding to the detection of these programs and information.

Measures to control (analyze) the protection of personal data should ensure that the level of protection of personal data processed in the information system is monitored by carrying out systematic measures to analyze the security of the information system and to test the operation of the personal data protection system.

Measures to protect the virtualization environment should prevent unauthorized access to and manipulate personal data processed in the virtual infrastructure and / or virtual infrastructure components, including virtual infrastructure management tools, virtual machine monitor (hypervisor), storage system (including the storage of images of virtual infrastructure), data networks through elements of a virtual or physical infrastructure, guest operating systems, virtual containers, the system and the replication network, terminal and virtual devices, as well as the backup system and the copies it creates.

Measures for the protection of technical means must exclude unauthorized access to stationary facilities that process personal data, facilities that support the operation of the information system (hereinafter means of operation), and to the premises in which they are permanently located, the protection of technical means from external influences, and also the protection of personal data presented in the form of informative electrical signals and physical fields.

Measures to protect the information system, its facilities, communication systems and data transmission should ensure the protection of personal data in the interaction of the information system or its individual segments with other information systems and information and telecommunications networks through the application of the architecture of the information system and design solutions aimed at ensuring the safety of personal data.

Measures to manage the configuration of the information system and personal data protection systems should provide management of changes in the configuration of the information system and personal data protection system, analyze the potential impact of the planned changes on the security of personal data, and document these changes.

These measures to ensure the security of personal data are implemented in the system of personal data protection for all objects and entities of access at the hardware, system, application and network levels, as well as in the environment of virtualization and cloud technologies.

When using information security tools certified in accordance with the requirements of information security in the informatization system of personal data "Rosmed.info" to ensure the 3 levels of protection of personal data, the following should be applied:

- Means of computer technology no lower than Class 5;
- Intrusion detection systems and anti-virus protection tools of at least Class 4 protection;
- Internetwork screens of at least 3 protection classes.

